5. STUDY CONDUCT

5.1 **Restrictions during the study**

The patients should observe the following items during the study.

- 1. The subject must fast before blood sampling for biochemistry test and undergoing EGD according to the procedures specified by the study centre.
- 2. 50 mg of gefarnate should be taken orally twice a day from randomized day to the last day of scheduled visit or day of discontinuation.
- 3. The subject must not stop the dosing temporarily and change the dose of LDA from informed consent day to the last day of scheduled visit or study discontinuation. As an exception, if the investigators judge that the temporarily stop dosing is necessary for treatments, e.g. biopsy, the subject can stop the LDA dosing temporality within consecutive 7 days.
- 4. The subject must maintain effective contraception from informed consent day to the last day of scheduled visit or day of discontinuation as judged by the investigator(s) during the study period.
- 5. The subject must not donate blood from informed consent day to the last day of scheduled visit or day of discontinuation.

5.2 Subject enrolment and randomisation method

The Principal Investigator will:

- 1. Obtain signed informed consent from the potential subject before any study specific procedures are performed.
- 2. Assign potential subject a unique enrolment number, beginning with 'E'. The Enrolment code (EXXXXYYY) is composed of 4 digits (XXXX) of centre number and 3 digits (YYY) of consecutive number in order of registration to screening at each study site. For the subjects who are confirmed having gastric and/or duodenal ulcer by EGD at screening and re-enrolled after the subjects are confirmed healing and provide informed consent for the second time, the number added 500 to the previous consecutive number (YYY) will be allocated. The number added 600, 700, 800 and 900 will be allocated at the third, the fourth, the fifth and sixth time correspondingly. For centre number(s), see Appendix A "Investigators and Study Administrative Structure".
- 3. Determine subject eligibility. See Sections 4.1 and 4.2
- 4. If the subject is eligible, the investigator(s) will enter the necessary information in the subject registration form via the subject registration Web system.
- 5. The subject registration will be completed after the eligibility checks by the subject registration Web system. A randomization code (Subject number) will be allocated automatically and will be shown on the screen in the Web system.
- 6. After obtaining the randomisation code (Subject number), the investigator(s) will start administration of the investigational product to the registered subject. The investigator(s) will print out the registration confirmation form and keep in the investigator's study file (See Section 9.4.1)

If a subject withdraws from participation in the study, then his/her enrolment/randomisation code cannot be reused.

The flowchart for subject registration, randomisation and prescription of the investigational product is shown in Figure 3.

Figure 3 Flow chart for subject registration and prescription of the investigational product

Procedure conducted at the study site

If a Randomisation code is assigned incorrectly, no attempt should be made to remedy the error once investigational products were dispensed. The subject will continue with the allocated randomised code and investigational products. AstraZeneca should be notified as soon as the error is discovered. Randomisation of subsequent subjects will continue using the first unallocated Randomisation code in the original sequence.

The investigational product given to individual subjects will be determined by a randomisation schedule. The details of the treatment allocations are described in "Procedures for drug accountability".

5.3 Procedures for handling subjects incorrectly enrolled or randomised or initiated on investigational product

Subjects who fail to meet the inclusion/exclusion criteria should not, under any circumstances, be enrolled or randomised. There can be no exceptions to this rule.

Where subjects that do not meet the selection criteria are randomised in error or incorrectly started on treatment, or where subjects subsequently fail to meet the study criteria post initiation, a discussion should occur between the AstraZeneca Study Delivery Team Physician and the Investigator regarding whether to continue or discontinue the subject from treatment.

The AstraZeneca Study Delivery Team Physician is to ensure all such decisions are appropriately documented. In situations where an agreement cannot be reached, the subject should have their study therapy stopped.

5.4 Blinding and procedures for unblinding the study

5.4.1 Methods for ensuring blinding

This study will be performed under double-blind conditions. The closest attention should be paid to make the appearance, package and labelling of the investigational products indistinguishable. The investigational product will be allocated by the responsible person who is not related to this study.

5.4.2 Methods for unblinding the study

Individual treatment codes, indicating the treatment randomisation for each randomised subject, will be available to the investigator(s) and the personnel who are independent to the study evaluation at the Drug Safety Department, AstraZeneca.

The treatment code should not be broken except in medical emergencies when the appropriate management of the subject requires knowledge of the treatment taken actually. The investigator documents and reports the action to AstraZeneca, without revealing the treatment given to subject to the AstraZeneca staff.

AstraZeneca retains the right to break the code for SAEs that are unexpected and are suspected to be causally related to an investigational product and that potentially require expedited reporting to regulatory authorities. Treatment codes will not be broken for the planned analyses of data until all decisions on the evaluability of the data from each individual subject have been made and documented.

5.5 Treatments

5.5.1 Identity of investigational product(s)

Formulation, content, and manufacturer of the investigational products are described in Table 3.
Investigational product	Dosage form and strength	Formulation number	Manufacturer
D961H capsule 20 mg	Hard capsule containing 22.3 mg of D961H as enteric coated pellets.	H1189-04-01	AstraZeneca Sweden Operations Drug Product Supply
D961H placebo capsule	Hard capsule unidentifiable to D961H capsule 20 mg	H0459-06-03	AstraZeneca Sweden Operations Drug Product Supply

Table 3Investigational product

Packaging of the investigational product

Fourteen capsules of D20 or placebo will be packed in a blister pack and it will be packed in an aluminium pouch under the responsibility of investigational products, AstraZeneca R&D Mölndal, Sweden. Sixteen aluminium pouches (224 capsules in total) will be packed in a paper box.

5.5.2 Doses and treatment regimens

One capsule of the investigational product will be orally given once daily after breakfast for the period of 72 weeks. The investigator(s) must instruct the patients to take the investigational product regardless the time on the day of the first prescription and take the investigational product after examination on the days of EGD and biochemistry test conducted.

5.5.3 Additional study drug

Table 4Mucosal protectant

Drug name	Dosage form and strength	Manufacturer
Gefanil Capsule 50 [®]	1 capsule containing Gefarnate 50 mg	Dainippon Sumitomo Pharma Co. Ltd

Doses and treatment regimens

From randomized day to the last day of speculated visit or day of discontinuation, a capsule of gefarnate 50 mg should be taken orally twice a day (after breakfast and after dinner). On the day of the first prescription, dose should be adjusted considering randomization time. Gefarnate should be taken after examination on the days of EGD and biochemistry test conducted.

5.5.4 Labelling

Labels will be prepared in accordance with Good Manufacturing Practice (GMP) and local regulatory guidelines. The labels will fulfil GMP Annex 13 requirements for labelling. Label text will be translated into local language.

The label will include the following information: the description of name of the investigational product, study code, batch number, quantity, expiry date, storage condition, randomisation code, instruction, name of sponsor and address and 'for clinical study use'. Details of labelling study drug will be described in a separate document, "Storage conditions of investigational products".

5.5.5 Storage

All study drugs should be kept in a secure place under appropriate storage conditions. The investigational product label on the pack specifies the appropriate storage.

A description of the appropriate storage conditions is specified in the document 'Procedures for drug storage'.

5.6 **Concomitant and post-study treatment(s)**

Other medication, which is considered necessary for the subject's safety and well being, may be given at the discretion of the investigator and recorded in the appropriate sections of the eCRF.

5.6.1 Allowed concomitant treatments

Drugs used for pre-treatment of EGD (e.g. local anaesthetic, anticholinergic agents, antianxiety agents or sedative drug). Any drugs used for pre-treatment are not to be recorded in the eCRF.

5.6.2 **Prohibited concomitant treatments**

The following treatments cannot be used concomitantly after randomization:

- (i) PPIs (except for investigational product)
- (ii) H2-receptor antagonists
- (iii) M1-receptor antagonists
- (iv) *H. pylori* eradication therapy
- (v) Antacids
- (vi) Prostaglandin analogue indicated for peptic ulcers (e.g. Misoprostol)
- (vii) Drugs with systemic anticholinergic effects (except for butylscopolamine bromide used for pre-treatment of EGD)
- (viii) Gastrointestinal promotility drugs
- (ix) Any drug known to have drug-drug interactions with D961H and/or OPZ (e.g atasanavir sulphate, diazepam, [use for pre-treatment before EGD is acceptable],

phenytoin, warfarin, tacrolimus hydrate, digoxin, methyldigoxin, itraconazole, gefitinib, voriconazole)

- (x) Anticancer drugs
- (xi) More than 8 days continuous NSAID therapy (oral, intravenous, intramuscular or suppository)
- (xii) Anticoagulants (warfarin, vitamin K antagonists, heparin, lowmolecular weight heparin, anti-thrombin drug or anti Xa drug)
- (xiii) Mucosal protectants (except for the ones provided by the sponsor)

5.7 Treatment compliance

The administration of all medication (including investigational products) should be recorded in the appropriate sections of the eCRF.

Compliance with the investigational product and mucosal protectant

The investigational product and mucosal protectant will be prescribed every visit. Treatment compliance will be verified by checking the number of remaining capsules returned. If the compliance rate is low because the subject missed taking capsules, and so on, the investigator(s) must instruct the subject to follow the instruction.

Compliance with LDA

The subjects will be asked to record the daily compliance status for LDA administration on the compliance record and bring it (See Appendix F) at each visit. If the compliance rate is low because the subject missed taking tablets, and so on, the investigator(s) must instruct the subject to follow the instructions.

5.7.1 Accountability

AstraZeneca will provide the study documents 'Procedures for drug accountability' and 'Procedures for drug storage', which describe the specific requirements.

Investigational product will not be distributed to the study site until the contract is concluded between the study site and AstraZeneca. The investigational product provided to the study site must only be used for the purpose and the dosage as directed by the clinical study protocol.

The investigator(s) and/or the Investigational Product Storage Manager must instruct the subject to return unused D961H capsule and Gefanil Capcel 50[®]. The investigator(s) and/or the Investigational Product Storage Manager must also confirm the number of capsules returned and recorded in the 'Investigational Product Log'. If there is any discrepancy in the number of capsules prescribed, administered, and returned, the investigator(s) or the study coordinator must confirm the reason with the patient and record it in the eCRF. The

Investigational Product Storage Manager and the monitor must confirm that all unused and remaining investigational products are returned to AstraZeneca.

The Investigational Product Storage Manager is responsible for managing the unused investigational products and remaining investigational products returned from the patients from distribution to the study site until the return to AstraZeneca.

5.8 Discontinuation of investigational product

The study treatment and assessments can be discontinued at any time.

Specific reasons for discontinuing a subject from this study are:

- Voluntary discontinuation by the subject who is at any time free to discontinue his/her participation in the study, without prejudice to further treatment
- Safety reasons as judged by the investigator(s) and/or AstraZeneca
- Severe non-compliance to protocol as judged by the investigator(s) and/or AstraZeneca
- Incorrect enrolment i.e., the subject does not meet the required inclusion/exclusion criteria for the study except for the cases that the AstraZeneca Study Delivery Team Physician and the Investigator reach an agreement to continue the study as the result of the discussion. (See also Section 5.3)
- Subject lost to follow-up
- Occurrence of an event in conflict of exclusion criteria (e.g., pregnancy)
- Development of gastric and/or duodenal ulcer
- Difficulty to conduct the study as judged by the investigator(s) due to the presence of gastric and/or duodenal mucosal lesion such as bleeding.
- Stopping treatment with daily LDA
- Others as judged appropriate by the investigator(s) (reasons for discontinuation must be documented in the eCRF appropriately)

5.8.1 Procedures for discontinuation of a subject from investigational product

A subject that decides to discontinue investigational product will always be asked about the reason(s) and the presence of any adverse events. If possible, they will be seen and assessed by an investigator(s). Adverse events will be followed up at the discretion of the investigator (See Sections 6.4.3 and 6.4.4). Compliance records, study drug and mucosal protectant should be returned by the subject.

If a subject is withdrawn from study, see Section 5.9.

For Japan, replace the above paragraph with the paragraph below

A subject that discontinues will always be asked about the reason(s) for discontinuation and the presence of any adverse events. The Principal Investigator/sub-investigator will perform the best possible observation(s), test(s) and evaluation(s) as well as give appropriate medication and all possible measures for the safety of the subject at the discretion of the investigator. They will also immediately inform AstraZeneca of the withdrawal. Adverse events will be followed up (See Sections 6.4.3 and 6.4.4). Compliance records and study drug should be returned by the subject.

5.8.2 Procedures for subjects study completion before 72 weeks

When100 subjects or above who have taken the investigational products for 52 weeks or more are achieved and the comparative analysis (interim and/or final) has been completed, the study will be finished before 72 week. (See Figure 1) AstraZeneca will announce the study termination to the investigator(s) as soon as possible. The investigator(s) should inform the subjects of the termination and perform the withdrawal/study completion visit (Visit 20) assessments at the next visit after the key broken.

If the number of subjects who have taken the investigational products for 52 weeks or more is less than 100 after key break, the study will continue. AstraZeneca will report the continuation of the study and the randomised drug for each subject to the investigator(s). The investigator(s) should notice subjects who should complete the study (see Figure 1) and perform the withdrawal/study completion visit (Visit 20) assessments to them at the next visit after the key broken of efficacy analysis. Subjects who are fulfilled with the criteria of the study continuation (see Figure 1) will continue to take the investigational product after the investigator(s) should confirm the continuation of the investigational treatment with them. If subjects wish to terminate the study at the next visit after the key broken, the subjects will complete the study after the withdrawal/study completion assessments (Visit 20).

AstraZeneca will report the termination of the study to investigator(s) as soon as the number of subjects who have taken the investigational products for at least 52 weeks is 100 or more.

Subjects should take the investigational product and mucosal protectant until the last visit, the next visit after the key broken, as general rule.

5.9 Withdrawal from study

Subjects are at any time free to withdraw from study (investigational product and assessments), without prejudice to further treatment (withdrawal of consent). Such subjects will always be asked about the reason(s) and the presence of any adverse events. If possible, they will be seen and assessed by an investigator. Adverse events will be followed up at the discretion of the investigator (See Sections 6.4.3 and 6.4.4). Compliance records, study drug and mucosal protectant should be returned by the subject.

6. COLLECTION OF STUDY VARIABLES

6.1 Recording of data

The Rave Web Based Data Capture (WBDC) system will be used for data collection and query handling. The investigator will ensure that data are recorded on the electronic Case Report Forms as specified in the study protocol and in accordance with the instructions provided.

The investigator ensures the accuracy, completeness, and timeliness of the data recorded and of the provision of answers to data queries according to the contract or Clinical Study Agreement with applicable information. The investigator will electronic sign the completed electronic Case Report Forms. A copy of the completed electronic Case Report Forms will be archived at the study site.

For Japan, add the below paragraph

The Principal Investigator/sub-investigator will record data on the observations, tests and assessments specified in the protocol on the electronic CRFs provided by AstraZeneca. The eCRF will be accompanied with 'Instructions for the Investigator', which should be followed. These instructions provide guidance for the recording of study data in the eCRF including how to change data incorrectly recorded.

6.2 Data collection and enrolment

6.2.1 Recording of demographic characteristics and screening test

The data on the following demographic characteristics and the screening test are collected, and recorded in eCRF.

Visit 1 (within 2 weeks of randomization)

- Patient background (sex, date of birth, race, smoking habit or not, drinking habit or not, height, body weight)
- Primary disease (disease that requires continued LDA administration), history of ulcer (presence or absence of definite diagnosis in the past), history of *H. pylori* eradication, history of disease (critical symptom & finding in the past, though currently cured), incidental disease (disease currently under treatment [including the disease that is controlled by treatment]), history of operation, concomitant therapy & concomitant drug
- Physical findings, vital signs (blood pressure and pulse rate)

- EGD (see Section 6.2.2. The test results obtained by 2 weeks before randomization but before acquisition of informed consent may be used if the consent in this regard is obtained.)
- Blood test, blood biochemical test
- Urine tests
- Pregnancy test by urinalysis (hCG) (only the fertile females before menopause)

Visit 2 (randomization day)

- Physical findings
- Assessment of gastrointestinal symptoms attributable to LDA in the past 7 days (Section 6.3.4)
- *H. pylori* test (see Section 6.2.3)
- CYP2C19 gene test (see Section 6.8)
- Adverse events, incidental disease
- Concomitant therapy & concomitant drugs

6.2.2 EGD

EGD should be performed according to standard procedure in each study centre. Any drugs used for pre-treatment are not to be recorded in the eCRF.

6.2.2.1 Presence or absence of onset of gastric or duodenal ulcer

Refer to Section 6.3.1.

6.2.2.2 Degree of lesion in gastric mucosa

Refer to Section 6.3.2.

6.2.2.3 Presence/absence and severity of reflux esophagitis

Refer to Section 6.3.3.

6.2.3 *H. pylori* test (IgG antibody)

The blood (2 mL) is collected at visit 2 to determine IgG antibody and to diagnose the presence or absence of *H. Pylori* infection. If it is not possible to collect the blood at visit 2, the blood sample may be collected on patient's visit by the time of discontinuation or termination of study period. *H. pylori* test (IgG antibody) and CYP2C19 should be done at same visit as a general rule. The samples are collected and determined by

6.3 Efficacy

6.3.1 Presence or absence of onset of gastric or duodenal ulcer

EGD is performed under fasting condition on the visits 1, 5, 8, 11, 14, 17 and 20 (at the time of screening, 12 weeks after randomisation, every 12 weeks thereafter) to check the presence or absence of gastric or duodenal ulcer. EGD can be performed if the patient have symptoms or signs indicating an unscheduled EGD as well. If any ulcer is detected in the stomach or duodenum, the site and the longest diameter of ulcer are recorded in eCRF. If plural number of ulcers are detected, the largest site and the longest diameter of ulcer are recorded in the eCRF.

Presence or absence of gastric or duodenal ulcer:

It is judged that ulcer is present when the following findings are obtained in EGD.

[Mucosal defect of 3 mm or more. Accompanied by the ulcer bottom with annular or ovalshaped white fur. The borderline of ulcer bottom margin is clear and not irregular. There is no tumor lesion and no malignant finding.]

Site

Site I: Cardia, fundus, upper body, middle body, lower body, angular region, pyloric antrum, bulb, bulb posterior

Site II: Anterior wall, posterior wall, greater curvature, lesser curvature

Diameter of ulcer

The long diameter of ulcer is determined with reference to endoscopic forceps, etc.

Photography of EGD

For the central judgment to confirm the presence of ulcer in the stomach or duodenum, EGD photos of the site judged as the ulcer scar at the time of screening and those of the site judged as ulcer during the investigational product administration period (2 close-up shots and 1 long shot as a general rule. The same applies to the case when EGD photos taken in the past is used because the scar is ambiguous) are submitted to the sponsor. If plural number of ulcers are observed, EGD photos of the largest ulcer are submitted to the sponsor. In all cases, mask any private information (name, chart No., etc.) that can specify the subject before submission of photos to the sponsor.

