12.2.1 Primary variable

The primary variable of this study is the time from randomisation to a occurrence of gastric and/or duodenal ulcer. Both FAS and PPS will be used for the analyses of the primary variable, but the primary analysis will be based on the FAS. In addition, a secondary analysis for the primary variable will be done using the FAS excluding the data of subjects who are judged not to have an ulcer scar by the central evaluation committee at baseline (see Section 12.4). In this analysis, the evaluation of the central committee for the presence/absence of gastric and/or duodenal ulcer after randomisation will be used.

If a occurrence of gastric and/or duodenal ulcer is confirmed by EGD, then the occurrence will be defined as an event. The time from the randomisation to the occurrence of the peptic ulcer will be analysed using the Kaplan-Meier method and shown as graphs. For subjects who have no occurrence of peptic ulcer throughout the study, they will be treated as censored at the timing of the last EGD. The time-to-event curves will be compared between D20 and placebo using a log-rank test.

As a secondary analysis, the primary variable will also be analysed based on a Cox proportional hazard model including effects of sex, age, *H. Pylo*ri status, dose of LDA and CYP2C19.

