12.4 Central evaluation committee and independent data monitoring committee

12.4.1 Central evaluation committee

A central evaluation committee consisting of gastrointestinal specialists will be appointed for this study to validate the diagnosis by the investigator based on the EGD findings.

The central evaluation committee will review EGD findings regarded as ulcer scar, past EGD findings used for diagnosis in case of unclear scar, and EGD findings on the bases of which the investigator made a diagnosis of gastric or duodenal ulcer after starting the study treatment, as appropriate, for all subjects randomized to the investigational product. The central evaluation committee will report the review results to the sponsor.

The timing of meetings and responsibilities of the central evaluation committee will be specified separately.

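### With several ulcers only the largest is sent for central review, so the secondary centrally read analyses can lose a true event

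*Protocol*

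**What the plan says.** Protocol 6.3.1 defines an ulcer by four elements: a size threshold ("Mucosal defect of 3 mm or more"), a base with white coating, a clear and regular margin, and no tumour or malignant finding. It gives the purpose of the photos as "For the central judgment to confirm the presence of ulcer in the stomach or duodenum".

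For a subject with more than one ulcer, the same section limits both data streams to one lesion:

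- eCRF: "If plural number of ulcers are detected, the largest site and the longest diameter of ulcer are recorded in the eCRF".
- Photos: "If plural number of ulcers are observed, EGD photos of the largest ulcer are submitted to the sponsor".

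Section 12.4.1 has the committee review "EGD findings on the bases of which the investigator made a diagnosis of gastric or duodenal ulcer after starting the study treatment". In the secondary analysis of the primary variable (12.2.1), "the evaluation of the central committee for the presence/absence of gastric and/or duodenal ulcer after randomisation will be used". Section 12.2.2.1 does the same for the ulcer-free rates. Section 5.8 lists development of an ulcer among the reasons for discontinuing a subject.

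**The concern.** The centrally read analyses ask one question per subject: was an ulcer present or not? In a subject with several ulcers, the committee must answer from one lesion, chosen by size. The protocol states no step for looking at the other lesions if that one is rejected. A subject with a qualifying smaller ulcer can then be classed as having none and, under the censoring rule in 12.2.1, be censored at the last EGD.

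At stake is the accuracy of the protocol's own check on an endpoint that is read locally at about 60 centres. That check is a secondary analysis. The primary result does not depend on it.

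**Working it through.** **Step 1: when can the rule cause an error?** Take a subject whose largest lesion is rejected by the committee.

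- *Rejected because it is under 3 mm.* Every other lesion is smaller and fails too. The verdict of no ulcer is right.
- *Rejected on base, margin or tumour-like appearance, and no other lesion meets the definition.* The verdict is again right.
- *Rejected on base, margin or tumour-like appearance, and another lesion of 3 mm or more meets all four elements.* The verdict is wrong, and the committee has not been sent the photos that would show it.

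Only the third case is an error. It is possible because, above 3 mm, being larger does not make a lesion more likely to satisfy the other three elements.

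**Step 2: can the event come back later?** It is unlikely. The investigator has diagnosed an ulcer, which is a discontinuation reason in 5.8, so scheduled EGDs normally end. The other lesion's site and diameter are not in the eCRF.

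**Step 3: which analyses use the central verdict?**

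| Item | Protocol section | Uses the central verdict? |
|---|---|---|
| Primary log-rank test, FAS | 12.2.1 | No; an event is an ulcer confirmed by EGD |
| 18- and 36-event triggers | 3.1, 12.2.3, 12.3 | No |
| Interim analysis | 12.2.3 | No centrally read test described |
| Secondary analysis of the primary variable | 12.2.1 | Yes |
| Secondary analysis of ulcer-free rates | 12.2.2.1 | Yes |

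**Step 4: how large is the loss?** The protocol gives no figure to reproduce and no rates. Let m be the share of ulcer subjects with two or more ulcers, r the share of largest lesions rejected, and c the chance that another lesion then qualifies. All three are assumptions. The base of 36 events comes from 12.3.

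Expected events lost = 36 × m × r × c

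| Assumptions | Low end | High end |
|---|---|---|
| m 15–40%, r 10–25%, c 50% | 36 × 0.15 × 0.10 × 0.5 = 0.27 | 36 × 0.40 × 0.25 × 0.5 = 1.8 |
| m 10–50%, r 5–20%, c 50–100% | 36 × 0.10 × 0.05 × 0.5 = 0.09 | 36 × 0.50 × 0.20 × 1.0 = 3.6 |

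By Step 1, r should count only rejections on non-size grounds, so a rate that includes size rejections overstates the loss.

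**Step 5: would that weaken the secondary test?** The protocol states no power for it, so the design assumptions in 12.3 serve as a yardstick: 6-month rates of 1.5% and 7.4%, two-sided 2.94%. With exponential times the hazard ratio is ln(0.985)/ln(0.926) = 0.197. Power is Φ(|ln HR| × √d / 2 − 2.178) by Schoenfeld and Φ(√d × (1 − HR)/(1 + HR) − 2.178) by Freedman.

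- d = 36: 99.7% (Schoenfeld), 96.8% (Freedman).
- d = 32, that is 3.6 lost events rounded up to 4: 99.2% and 94.7%.

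Even the top of the second range would cost little power.

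**The case against.** The best defence is that the rule does little harm and may not be the whole procedure.

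- *Choosing the largest lesion is sensible.* It removes size as a source of wrong rejections. This stands, but it leaves the other three elements.
- *Further review is not excluded.* Section 6.3.1 limits what is submitted, not what is photographed. Section 12.4.1 speaks of EGD findings and adds: "The timing of meetings and responsibilities of the central evaluation committee will be specified separately". The long shot of the largest ulcer might also show a neighbouring lesion. This stands as a possibility. A committee document, however, cannot guarantee images that sites were told not to send.
- *Recovery is not impossible.* A footnote to Table 2 asks discontinuing subjects to have the Visit 20 tests where possible, and these include EGD. This stands, so the loss is unlikely to be recovered rather than certain to be permanent.

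Three stronger readings are tempting, and the protocol does not support them.

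- A reader might infer that the rule threatens the primary result or the interim analysis. Step 3 shows that neither uses the central verdict.
- A reader might infer a material shift in the hazard ratio, because D20 is expected to have few events. The expected D20 share is ln(0.985)/[ln(0.985) + ln(0.926)] = 16.4%, or about 5.9 of 36. The first range then implies an expected loss of 0.27 × 0.164 = 0.04 to 1.8 × 0.164 = 0.30 D20 events, well short of one. Committee review is blinded (3.1) and the submission rule is the same in both arms, so there is no stated reason for unequal loss.
- A reader might infer that the gastric/duodenal split is compromised. Every objective and endpoint combines the two sites, and 12.2.2.1 lists no subgroup by ulcer site.

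It is also true that central review can only remove events, because only investigator-diagnosed ulcers are reviewed. That follows from 12.4.1 and not from the largest-lesion rule. Changing the rule would remove only the avoidable part.

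**Conclusion.** The point holds as a minor weakness in data collection. Followed as written, 6.3.1 can lead the committee to class a subject with a qualifying ulcer as having none, and 12.2.1 and 12.2.2.1 then use that verdict. The error needs three things together: several lesions, rejection of the largest on a ground other than size, and another unsubmitted lesion that meets the definition.

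The size cannot be known from the protocol. It is about 0.3 to 1.8 of 36 events under the first set of assumed rates and 0.1 to 3.6 under the second. The effect is confined to the secondary centrally read analyses and is not expected to differ between arms. The primary FAS log-rank analysis, the event triggers and the interim analysis stand as planned.

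**What to change.** In 6.3.1, have sites submit photos of every lesion judged to be an ulcer and record site and diameter for each. State that the committee scores the subject positive if any submitted lesion meets the definition. At minimum, require the remaining photos before a subject is classed as having no ulcer.

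The cost is a few extra photos and eCRF lines, and only in subjects with several ulcers. Under the second set of assumptions that is 36 × 0.10 = 3.6 to 36 × 0.50 = 18 subjects. No added endoscopy or reader is needed. The change is best made before enrolment, because images not taken at the EGD cannot be obtained afterwards.
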